**Clinical Procedures**

**Table 1: Schedule of Testing for All Subjects (See Table 2 for Crossover Subjects' Testing)**

3 Months (90 days): 76-104 days - 4 Months (120 days):113 -127 days - 6 Months (180 days): 166-194 days - 12 Months (360 days): 330-390 days - 24 Months (720 days): 690-750 days - 36 Months (1080 days): 1050-1110 days

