- **Enrollment (consent) to 12-months post procedure:** all medications and all adverse events
  - **12 to 36 months post-procedure:** all medications and serious adverse events only. Previously reported adverse events will be followed up through resolution until the end of the study.
- h) **Renal Artery Imaging** will be performed at the 6-month post-procedure visit to assess if a renal artery stenosis is suspected. A renal duplex ultrasound (DUS) will be obtained at 6M and submitted to the DUS Core Laboratory. If the DUS is determined to be nondiagnostic a repeat DUS, a MRA, CT or angiogram will be performed (repeat imaging is recommended to be completed within 30 days after confirmation of non-diagnostic imaging). If evidence of a clinically significant stenosis is indicated by the DUS or MRA/CT Core Laboratories, an angiogram must be obtained and submitted to the Angiographic Core Laboratory.
- A renal duplex ultrasound (DUS) at 6-month follow-up is not required for subjects randomized to the control group who are crossing over, if they are having the renal denervation procedure done within 30 days of their 6 month follow-up visit. If they are not having the renal denervation procedure done within the 30 days of their 6 month follow-up visit, a renal duplex ultrasound (DUS) is required.
  - The 12-month renal imaging will be required for all randomized subjects. If the renal imaging is determined to be nondiagnostic, a repeat DUS, MRA, CTA or angiogram will be performed. If repeat DUS, CTA, or MRA is nondiagnostic or evidence of a clinically significant stenosis ( $>60$ - $70\%$ ) is indicated, an angiogram must be obtained and submitted to the Angiographic Core Laboratory. Subjects who have already completed their 12-month visit follow up at the time of protocol approval will be required to undergo renal imaging at their next scheduled follow-up visit unless they have a renal angiogram due to crossover. For participating sites in Germany and the UK, only DUS or renal MRA imaging at the 12-month follow-up visit (or 24M or 36M follow-up as applicable) will be performed. For these countries, if the initial DUS or initial renal MRA is non-diagnostic, a repeat DUS or repeat renal MRA should be performed. If the initial imaging modality or subsequent repeat(s) are non-diagnostic, the investigator should choose the repeat imaging modality (DUS or MRA) that is expected to yield the required information for a diagnostic study.

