All the safety endpoints will be adjudicated by the Clinical Events Committee (CEC). The following algorithm will be used to evaluate the safety event rates: The denominator will include all subjects who either had a CEC adjudicated event prior to the time of interest (180 days for 6 months events, for example), or had last contact date that is beyond the lower window of the follow up (166 days for 6 month events, for example). The numerator will include all subjects who had CEC adjudicated events up to the time of interest (180 days for 6 months events, for example). The secondary safety endpoints will be compared between treatment groups using Fisher's exact test. In addition, two-sided 95% confidence intervals of the difference between treatment groups will be presented. The secondary safety analyses will be performed using the ITT population defined in H1.

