All the safety endpoints will be adjudicated by the Clinical Events Committee (CEC). The following algorithm will be used to evaluate the safety event rates: The denominator will include all subjects who either had a CEC adjudicated event prior to the time of interest (180 days for 6 months events, for example), or had last contact date that is beyond the lower window of the follow up (166 days for 6 month events, for example). The numerator will include all subjects who had CEC adjudicated events up to the time of interest (180 days for 6 months events, for example).

The secondary safety endpoints, out to 6-months follow-up, will be compared between treatment groups using Fisher's exact test. Two-sided 95% confidence intervals of the difference between treatment groups will also be presented.

After 6-months follow-up, control subjects may crossover (undergo renal denervation), and secondary safety endpoints will be summarized by group (RDN, Crossovers, Non-Crossovers). RDN vs. Crossover vs. Non-Crossover groups will be compared out to 36 months post-procedure for the RDN and Non-Crossover groups and out to 24 months for the Crossover group using chi-square tests for categorical data and ANOVA for continuous data.

The secondary safety analyses will be performed using the ITT population defined in section 9.1.3.1.

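### The 6-month safety count closes at day 180, but the visit with the first scheduled stenosis scan may run to day 194, so a stenosis first seen on a compliant late scan is scored event-free at 6 months

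*SAP*

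**What the plan says.** SAP 9.9.2 introduces its rule with "The following algorithm will be used to evaluate the safety event rates" and sets the numerator as "The numerator will include all subjects who had CEC adjudicated events up to the time of interest (180 days for 6 months events". Protocol H.3 gives the same rule. A subject enters the denominator through an adjudicated event before the nominal day, "or had last contact date that is beyond the lower window of the follow up (166 days for 6 month events". Neither text requires a scan.

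Protocol Table 1 sets the visit windows: "6 Months (180 days): 166-194 days" and, for the last visit, "36 Months (1080 days): 1050-1110 days". Protocol F.7(h) places the renal duplex at the 6-month visit, and Table 1 shows no earlier scheduled post-procedure imaging. If the duplex is non-diagnostic, "repeat imaging is recommended to be completed within 30 days after confirmation of non-diagnostic imaging". A suspicious scan must be followed by an angiogram. Only controls who cross over within 30 days of the 6-month visit may omit the duplex.

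On comparisons, the SAP says "The secondary safety endpoints, out to 6-months follow-up, will be compared between treatment groups" by Fisher's exact test. It continues: "After 6-months follow-up, control subjects may crossover (undergo renal denervation), and secondary safety endpoints will be summarized by group (RDN, Crossovers, Non-Crossovers". Protocol H.3 compares the arms by Fisher's exact test and states no 6-month limit.

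**The concern.** The rule uses the lower edge of the visit window to admit subjects as evaluable but ignores the upper edge when counting events. That does little harm for a death or a stroke, which has its own date. A silent stenosis is different, because it is found when the artery is imaged and the first scheduled image may compliantly be taken after the count has closed. Such a subject adds to the denominator as event-free.

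At stake are the 6-month stenosis rate (SAP 5.2, protocol H.3) and the composite that contains it (SAP 5.2 and 9.9.2). Under the SAP, 6 months is also the last readout by randomised arm.

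**Working it through.** **Inputs.** Nominal days and windows come from protocol Table 1. The rule comes from SAP 9.9.2 and protocol H.3, whose days 180 and 166 are given as the 6-month example. Cuts at the other visits follow by analogy from the nominal days.

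**The plan's own figures.** 180 − 14 = 166 and 180 + 14 = 194. This matches the stated window, and its lower edge is the day 166 used in the rule.

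**Window days after the cut** = (upper limit − nominal day) ÷ (upper limit − lower limit + 1).

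| Visit | Window | Cut | Days after cut | Share |
|---|---|---|---|---|
| 3 months | 76–104 | 90 | 14 of 29 | 48% |
| 6 months | 166–194 | 180 | 14 of 29 | 48% |
| 12 months | 330–390 | 360 | 30 of 61 | 49% |
| 24 months | 690–750 | 720 | 30 of 61 | 49% |
| 36 months | 1050–1110 | 1080 | 30 of 61 | 49% |

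These are shares of permitted days. They equal shares of scans or samples only if visits spread evenly over the window, which the documents do not say.

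**The rule applied literally.** Numerator: event day ≤ cut. Denominator: in the numerator, or last contact after day 166.

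| Stenosis dated | Numerator, cut 180 | Denominator | Numerator if cut at 194 | 12-month numerator, cut 360 |
|---|---|---|---|---|
| Day 180 | yes | yes | yes | yes |
| Day 181, 190 or 194 | no | yes | yes | yes |
| Day 205 or 224 | no | yes | no | yes |

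Day 224 is the latest crossover angiogram that can replace a waived duplex: 194 + 30 = 224.

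**Dating.** The table dates the event to the scan itself. The endpoint requires angiographic confirmation, and the angiogram follows the scan. If events are dated to the angiogram, some scans taken before day 180 are missed as well. Only dating the event earlier than the scan would rescue days 181 to 194, and neither document does that.

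**Last timepoint.** At 36 months no later count exists. Protocol F.11 treats the first sample with a creatinine rise above 50% as the event, to be confirmed at least 21 days later. A rise first sampled on days 1081 to 1110 therefore enters no count.

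**The case against.** A fixed-day cut applied identically to both arms is a defined convention, and it does not of itself favour either arm. That stands: the direction of any effect on the between-arm difference is unclear. It does not answer the mismatch between the two edges of the window.

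Stenosis dating may be settled in the CEC Charter (protocol I.2.3), which is not among the documents. That also stands as a condition on the conclusion.

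Four stronger readings are tempting, and the documents do not support them.

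- A reader might infer that the primary safety result is compromised. SAP 9.9.1.1 allows at most 11 events in 253 (upper bound 7.09%), and a twelfth would fail (7.57%), so one omitted stenosis could in principle matter. But the algorithm sits under secondary safety, and SAP 9.9.1 and 9.9.1.1 do not say it governs the primary MAE. No 6-month stenosis rate is given, and protocol B.1.2 reports safety only to 3 months.
- A reader might infer that 6 months is the only imaged timepoint with a randomised comparison. That holds only under SAP 9.9.2. Protocol H.3 sets no such limit, and imaging is required again at 12 months.
- A reader might apply the rule to the 12-month stenosis evaluation in SAP 9.9.2.1. That section is descriptive and does not invoke the algorithm.
- A reader might extend protocol F.11's dating to the endpoint of a 40% or greater fall in eGFR. F.11 does not mention that endpoint.

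**Conclusion.** Wrong as written. Followed literally, the rule scores as event-free at 6 months a subject whose stenosis is first seen on a compliant scan on days 181 to 194. The bias in the 6-month stenosis and composite rates is downward. Its size cannot be derived, because the documents give neither a 6-month stenosis rate nor the distribution of scan days.

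This rests on the CEC dating a stenosis no earlier than the scan that first shows it. For secondary endpoints before 36 months the event moves to the next count. At 36 months a late-window creatinine event drops out altogether. The primary MAE is affected only if this algorithm is applied to it.

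SAP 9.9.2 and protocol H.3 also differ on whether the two-arm comparison continues after 6 months, and they need to be reconciled.

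**What to change.** In SAP 9.9.2 and protocol H.3:

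- For stenosis found on imaging (alone and within the composite) and for laboratory-detected events, date the event to the first abnormal image or sample.
- Count these events to the upper limit of the visit window in both arms: day 104, 194, 390, 750 or 1110. This applies whenever confirmation or adjudication is completed.
- Put anyone in the numerator in the denominator too. All other events keep the nominal-day cut.
- Report by arm the number with no diagnostic image by the upper limit, including controls whose duplex was waived for crossover.
- Show stenoses first seen after day 194, on a repeat scan or the pre-ablation crossover angiogram, only as a sensitivity analysis. Counting them in the main rate would give controls a longer window and a more direct test than the denervation arm.

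In SAP 9.9.1.1, state whether this rule governs the 6-month stenosis component of the primary MAE. If that is decided after the data were seen, label it post hoc and show it beside the day-180 count.

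The cost is wording, programming and a small table. The 6-month change needs no new data. At 36 months, confirmation of a late sample could fall on days 1102 to 1131 (1081 + 21 to 1110 + 21), and the documents do not say whether that draw would be available. Rates may rise slightly, and these components would run 14 days longer than the others at 3 and 6 months, and 30 days longer at 12 to 36 months.

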## F.10 Crossover Procedures

Control subjects may crossover and receive renal denervation therapy at or after their 6 month follow-up visit. For the subjects who had already completed their 6 month visit, the decision to crossover must take place at their next in person visit. All subjects will have 30 days from the Crossover visit ( 6, 12, 24 , 36 month follow-up or Unscheduled visit ) to undergo the crossover procedure. Subjects who are more than 30 days from their 6, 12, 24 or 36 month, must complete a crossover Baseline visit prior to crossing over. Control subjects who are coming in for their scheduled 6, 12, 24 and 36 month follow-up visit do not need to come in for a crossover Baseline visit if all the required crossover Baseline procedures occurred, including lipid panel, hs-crp and uric acid blood tests. To crossover, the subject cannot meet any of the anatomical and glomerular filtration rate (eGFR) exclusion criteria, and cannot be pregnant, nursing or planning to become pregnant during the course of the study follow-up. Crossover subjects will undergo follow-up visits at 4 weeks, 3, and 6 months ( $\pm$  14 days) post-procedure and annually at 12 and 24 months ( $\pm$  30 days) post-procedure. Follow-up procedures post-crossover procedure are listed below. Subjects who do not meet required eligibility criteria for crossover on the day of the procedure will undergo follow-up visits according to their original follow-up schedule. Crossover will not be offered at a later time if it was declined by control subjects during the allowed 30-day window.

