#### 9.1.4. Crossover Procedures

Control subjects may crossover and receive renal denervation therapy at or after their 6 month follow-up visit. For the subjects who had already completed their 6 month visit, the decision to crossover must take place at their next in person visit. All subjects will have 30 days from the Crossover visit (6, 12, 24, 36 month follow-up or Unscheduled visit) to undergo the crossover procedure. Subjects who are more than 30 days from their 6, 12, 24 or 36 month, must complete a crossover Baseline visit prior to crossing over. Control subjects who are coming in for their scheduled 6, 12, 24 and 36 month follow-up visit do not need to come in for a crossover Baseline visit if all the required crossover Baseline procedures occurred, including lipid panel, hs-crp and uric acid blood tests. To crossover, the subject cannot meet any of the anatomical and glomerular filtration rate (eGFR) exclusion criteria, and cannot be pregnant, nursing or planning to become pregnant during the course of the study follow-up. Crossover subjects will undergo follow-up visits at 1, 3, and 6 months ( $\pm$  14 days) and annually at 12 and 24 months ( $\pm$  30 days) post-procedure.

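### In the SAP's three-group safety tables after 6 months, Non-Crossover rates of death, ESRD and stenosis are biased upward, because only controls free of these events can leave the group

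*SAP*

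**What the plan says.** SAP 9.9.2 splits secondary safety at month 6. Before it, the randomized arms are kept: "The secondary safety endpoints, out to 6-months follow-up, will be compared between treatment groups using Fisher's exact test", with confidence intervals for the difference. Beyond it they are not: "After 6-months follow-up, control subjects may crossover (undergo renal denervation), and secondary safety endpoints will be summarized by group (RDN, Crossovers, Non-Crossovers". These groups are then "compared out to 36 months post-procedure for the RDN and Non-Crossover groups and out to 24 months for the Crossover group"; the planned test for categorical outcomes is chi-square.

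The rate algorithm in the same section is cumulative: "The numerator will include all subjects who had CEC adjudicated events up to the time of interest". The denominator admits a subject with an earlier adjudicated event, or one who "had last contact date that is beyond the lower window of the follow up". No landmark, censoring at crossover or person-time is specified, and the term Non-Crossover is not defined.

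On who may cross, Protocol F.10 says "Control subjects may crossover and receive renal denervation therapy at or after their 6 month follow-up visit", and SAP 9.1.4 adds "To crossover, the subject cannot meet any of the anatomical and glomerular filtration rate (eGFR) exclusion criteria". Protocol F.10 returns controls found ineligible on the procedure day to their original schedule. The exclusions in Protocol D.2 include eGFR below 45 and stenosis above 50% in a treatable vessel.

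SAP 9.9.2 assigns all secondary safety analyses to the ITT population. Protocol H.3 plans Fisher's exact test between the treatment groups on ITT, with no cut-off at 6 months.

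**The concern.** Membership of the Non-Crossover group is settled by what happens after randomization, but its events are counted from the sham procedure. During months 0 to 6 nobody can cross over, so every control is at risk as a control. A control who dies in that period, or has an event that bars crossover, becomes a Non-Crossover by rule. A control who comes through without one and then crosses takes that follow-up out of the Non-Crossover denominator. This is immortal-time bias in the rate itself, and it remains if the chi-square test is dropped and the table is only descriptive.

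RDN subjects are all kept from day 0. At equal true risk, the Non-Crossover row would therefore show more deaths, ESRD and stenoses per subject than the RDN row. The stake is how long-term safety reads at 12, 24 and 36 months in data meant for regulatory submissions.

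**Working it through.** The plan gives no rate, power or sample size for the three-group comparison, so there is no figure to reproduce. The check applies the SAP's counting rule to controls with a known risk.

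**Step 1. Which events bar crossover**

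| Event before crossover | Bars crossover? | Basis |
|---|---|---|
| Death | Yes | Cannot attend |
| ESRD | Yes | Needs eGFR below 15 (Protocol L.5); exclusion is below 45 (D.2) |
| Stenosis above 70% | Nearly always | Exclusion is above 50% in a treatable vessel (D.2); a non-treatable vessel, or a stent placed at least 3 months earlier, might not bar |
| MI, stroke, hypertensive crisis | No | Not among the crossover conditions (F.10, SAP 9.1.4) |
| Vascular complication, embolic event, perforation, dissection | Not in themselves | Same |

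For events that do not bar crossover, a later crossover's event and that subject leave the Non-Crossover group together, so the rate is not inflated.

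**Step 2. Formula**

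Let S(t) be the probability that a control is free of barring events at month t, and c the share of event-free controls who cross at month 6. For T beyond 6 months the SAP rule gives

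Non-Crossover rate = [(1 − S(6)) + (1 − c)(S(6) − S(T))] / [(1 − S(6)) + (1 − c)S(6)].

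The true control risk is 1 − S(T). With rare events, a constant hazard and h the horizon in years, the ratio of the two is about

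[0.5/(1 − c) + h − 0.5] / h.

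At h = 1 and c = 0.5: (1.0 + 0.5)/1 = 1.50.

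| Assumed share crossing at 6 months | 12 months | 24 months | 36 months |
|---|---|---|---|
| 30% | 1.21 | 1.11 | 1.07 |
| 50% | 1.50 | 1.25 | 1.17 |
| 70% | 2.17 | 1.58 | 1.39 |

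A simulation of 165 controls at 1% per year agreed: 1.22, 1.47 and 2.14 at 12 months, or 1.2%, 1.5% and 2.1% against a true 1.0%.

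**Step 3. Full formula at a 6-month risk of 1% (assumed)**

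For c = 0.6 and T = 12: S(6) = 0.99 and S(12) = 0.9801, so (0.01 + 0.4 × 0.0099)/(0.01 + 0.4 × 0.99) = 0.01396/0.406 = 3.44%, against a true 1.99%.

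| | 12 months | 24 months | 36 months |
|---|---|---|---|
| True control risk | 1.99% | 3.94% | 5.85% |
| SAP rule, 40% cross | 2.64% | 4.58% | 6.48% |
| SAP rule, 60% cross | 3.44% | 5.36% | 7.24% |

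The ratios barely change for a 6-month risk of 0.5% or 2%.

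**Step 4. In counts**

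Take the 165 sham subjects (Protocol B.1.2) and suppose 2 barring events by month 6. Of the other 163, 60% (98) cross, leaving 65 + 2 = 67 Non-Crossovers. Months 6 to 12 add 65 × 2/165 = 0.8 events. The table shows 2.8/67 = 4.2%, against about 4/165 = 2.4% for the whole control arm.

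**Step 5. Dependence on the undefined term**

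Suppose 40%, 20% and 10% of those remaining cross at 6, 12 and 24 months. If Non-Crossover means never crossed, the 12-month factor is 0.8/(0.6 × 0.8 × 0.9) = 1.85. If it means not crossed by that visit, it is 0.8/0.6 = 1.33, or 0.8/0.48 = 1.67 when month-12 crossers are also removed. The sign is the same; the size is not.

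**Step 6. How much opposite selection would cancel it**

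At a 6-month risk of 1%, the hazard in the remaining Non-Crossovers, relative to all controls, would have to be:

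| Share crossing | 12 months | 36 months |
|---|---|---|
| 30% | 0.57 | 0.91 |
| 60% | No reduction suffices | 0.70 |

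**The case against.** Much can be said on the other side.

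- **The early control experience is not lost.** A reader might infer that the first six months of later crossovers count nowhere. They do count, in the randomized Fisher table to 6 months. What does drop out of the three-group table, with the Crossover row timed from denervation, is a pre-crossover MI, stroke or crisis in a subject who later crosses.
- **Not every control-arm death lands in Non-Crossover.** Deaths after crossover fall in the Crossover group.
- **The composite is not inflated as a whole.** Most of its components do not bar crossover. ESRD should be very rare by 6 months in subjects enrolled with eGFR of at least 45, so in practice the effect rests mainly on mortality.
- **The direction is conditional.** Crossover is voluntary. At 30% crossover, a hazard 9% lower in those who stay cancels the 36-month effect.
- **Events are rare.** At 1% per year, 165 controls give 165 × 0.01 × 0.5 = 0.825 expected deaths by month 6. The chance of none is exp(−0.825), about 44%, and then crossover at 6 months inflates nothing. Protocol B.1.2 reports one sham-group major safety event to 3 months, a stroke, which does not bar crossover.
- **The SAP names the ITT population.**

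The first five points limit the claim and are accepted. They do not remove it: the counting rule is biased as written, and possible self-selection is a second, unknown bias rather than a correction. The ITT label does not help, because splitting controls by something they do after randomization is not analysis as randomized.

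**Conclusion.** The concern holds for control deaths, ESRD and nearly all stenoses above 70% that precede crossover, and for the composite only through those components. Under a constant hazard equal in both arms, with crossover otherwise unrelated to risk, the Non-Crossover rate is overstated for any crossover share above zero. The size rests on assumed shares and event rates: about 1.2 to 2.2 times at 12 months and 1.07 to 1.39 times at 36 months for 30% to 70% crossing at 6 months. At 1% per year the 12-month shift is 0.2 to 1.1 percentage points.

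A reader might go further and conclude that the trial's safety finding is compromised, or that denervation must look safer in every long-term table. The documents support neither. The primary safety endpoint is a performance goal in denervated patients and does not use these groups, the comparisons to 6 months keep the randomized arms, and the direction depends on who chooses to cross. The matter is confined to secondary long-term tables, but it should be corrected.

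**What to change.** In SAP 9.9.2:

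- **(a)** Report the randomized RDN versus control ITT comparison at 12, 24 and 36 months, as Protocol H.3 plans. Use time-to-event estimates at 36 months. A control crossing after the 6-month visit is followed at most to about day 194 + 30 + 750 = 974, short of the 36-month window opening at day 1,050. The present denominator rule would therefore again drop event-free crossovers.
- **(b)** As support, replace the Non-Crossover row with a row for control follow-up before denervation. All controls contribute from the sham procedure and are censored at crossover; later events and time go to the Crossover row. Present Kaplan-Meier incidence or events per 100 patient-years. Alternatively, keep the Non-Crossover row but start its count at a 6-month landmark, and define whether it means never crossed or not crossed by that visit.
- State that censoring at a voluntary crossover may be informative, so (b) supports (a) and does not replace it.

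Under the constant-hazard assumption, censoring at crossover returns the control rate to its true value (1.99%, 3.94% and 5.85% in the example). The cost is SAP wording and table programming from dates already collected. The tables become time-based rather than simple counts, and (a) compares arms as assigned, with part of the control arm denervated.
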